## Methods

**Design:** The trial is a parallel arm cluster randomized controlled trial (RCT) conducted across 14 primary care sites in Ontario, Canada. Participating sites were randomized 1:1 to either a PT-led primary care model or the usual physician-led primary care model for hip and knee pain. Randomizing at the practice level, rather than the patient level, enabled full integration of PTs within the primary care team and minimized the risk of contamination between providers. This protocol and analysis plan is according to the Standard Protocol Items: Recommendations for Interventional Trial (SPIRIT) reporting guidelines. See Table 1 for an overview of the schedule of enrolment, interventions and assessments as recommended in the SPIRIT guidelines.

Table 1. Schedule of enrolment, interventions, and assessments.

	STUDY PERIOD						
	Enrolment or clusters	Allocation of clusters	Enrolment of patient participants	Post-allocation			Close-out
TIMEPOINT	Pre-intervention	Pre-intervention	0 (baseline)	3 mo.	6 mo.	9 mo.	12 mo.
ENROLMENT OF PRIMARY CARE SITES:							
Eligibility screen	X						
Informed consent	X						
Allocation to study group		X					
ENROLMENT OF PATIENT PARTICIPANTS:							
Eligibility screen			X				
Informed consent			X				
INTERVENTIONS:							
PT-led primary care				◆	—————→		
Usual care				◆	—————→		
ASSESSMENTS:							

Participant characteristics and demographic information			X				
Participant health and experiences outcomes (LEFS, pain intensity, EQ-5D-5L, PSEQ, PCS, TSK-11, PHQ-2)			X	X	X	X	X
Participant health and experiences outcomes (GROC, satisfaction, adverse events)				X	X	X	X
Health system and societal outcomes (provider encounters, EHR utilization, healthcare utilization, missed occupational activities, assistance required)				X	X	X	X
Implementation measures (timely access, PT as first point of contact, access to PT, hip/knee management)			X	X	X	X	X
Implementation measures (patient adherence)				X			
QUALITATIVE INVERVIEWS:							
Patient participants				X			

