A common concern in cluster RCTs is the risk of selection and recruitment bias, particularly when patient enrollment occurs after cluster assignment. To address this, we took efforts to invite consecutive patients with hip or knee pain to participate in the study, to ensure RAs who handled recruitment and consent were not familiar with the patients, and to apply inclusion and exclusion criteria consistently across all sites. We also provided identical trial information to all potential participants before obtaining consent, regardless of cluster. This meant that we did not reveal which study arm participants were in until after obtaining their consent.

**Patient Participant Recruitment:** During patient participant recruitment, medical secretaries screened patients to be invited to participate when they booked an appointment for hip or knee pain. As an additional strategy, potential participants were also identified any healthcare provider (HCP) when they sought care for their hip or knee pain during a clinical visit. Potential participants who were agreeable to being invited to participate were contacted by a study research assistant (RA) to explain the details of the study. Those who were interested in participating were asked to complete a consent form that was built into the baseline surveys in a secure data collection platform (REDCap, Research Electronic Data

Capture). If a potential participant requested to do this in-person, arrangements were made to meet with the RA who provided detailed written and verbal information about the study and obtained consent for participation from those patients who were interested. A verbal consent process was in place for those who preferred to do this over the phone or in a virtual meeting.

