**Data Analysis Plan**

All analyses will be by intention to treat principle. Descriptive statistics will be provided for baseline characteristics and outcomes using means (standard deviation) or medians (interquartile range) for continuous variables and frequencies (percent) for categorical variables. We will compare arms using linear mixed models and generalized estimating equations (GEE) to account for clustering and present the corresponding p-values. Analyses will be performed using SAS, version 9.4 (SAS Institute Inc; Cary, NC).

The estimand for patient health outcomes will be the time-specific patient participant treatment effect, adjusting for clustering by primary care site. The primary outcome (LEFS) will be analyzed using linear mixed regression with restricted maximum likelihood (REML) estimates under the assumption of Missing at Random (MAR), which will allow the use of all available data without the need for multiple imputation. The Kenward-Rogers degrees of freedom correction will be used to account for a small number of clusters. The 12-month timepoint will provide the intervention effect as the adjusted least square mean difference between arms with 95% confidence intervals. Secondary comparisons will be made using adjusted least square mean differences between arms at all intermediate time-points. Fixed effects in the mixed model will include time, intervention group by time interaction (omitting the group main effect), pre-specified covariates associated with hip and knee function (patient participant age, sex, duration of current episode of hip or knee pain, income, highest level of education, and comorbidity score), and primary care site rurality and number of active patients (the covariates from the covariate-constrained allocation procedure). Repeated measures will be modeled using a covariance structure determined by information criteria (AIC/BIC). Clinic site will be included as a random effect to account for site clustering. We will assess for potential risk of bias associated with missing data by comparing the characteristics of those who participated. We plan to carry out a sensitivity analysis for a potential departure of our MAR assumption using a delta-adjusted imputation pattern mixture model approach. This approach will allow us to investigate the robustness of our trial outcomes with regard to the missing values of the LEFS.

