We plan a secondary analysis using our primary outcome (LEFS) to compare the proportion of participants who experience a meaningful improvement in each arm (responder analysis). We will define a meaningful change as an improvement of greater than or equal to 9 points on the LEFS (the minimally important change). We will present the proportion of participants who experience a meaningful improvement in each arm and compare, using relative risk, between groups using robust Poisson regression, accounting for clustering. We will use empirical covariance (“sandwich”) bias-adjusted (residual-based) estimators, and apply the Fay and Graubard correction for the small number of clusters.

Pain intensity (NPRS), quality of life (EQ-5D-5L), self-efficacy (PSEQ), catastrophic thinking (PCS), pain-related fear (TSK)-11, and depressive symptoms (PHQ-2) will be analyzed using the same analytic approach as described for our primary LEFS analysis, adjusted for the same covariates. We will use simple mean imputation to fill in missing individual items on surveys as described by Chavance. Patient satisfaction and global rating of change do not include a baseline measure and will be assessed using ordinal logistic regression with random effects and adjusting for the same covariates as above.

Incidence rates for minor adverse events (yes or no) will be calculated using robust Poisson regression and compared by calculating relative risks with confidence intervals using GEE-type robust covariance estimators (PROC GLIMMIX, EMPIRICAL option in SAS) to account for clustering. In our models comparing incidence rates, we will use an exchangeable working correlation matrix, empirical covariance (“sandwich”) bias-adjusted (residual-based) estimators, and the Fay and Graubard correction

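### The global rating of change model adjusts for no baseline severity measure, although LEFS and pain are collected at baseline; adding them would protect against imbalance between 7 and 7 sites at almost no cost

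*Combined protocol and SAP*

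**What the plan says.** Objective 1 lists global rating of change and patient satisfaction among the effectiveness outcomes. Both are collected at follow-up only. The Data Analysis Plan states: "Patient satisfaction and global rating of change do not include a baseline measure and will be assessed using ordinal logistic regression with random effects", and then "adjusting for the same covariates as above".

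The list referred to is the one for the LEFS model. At participant level it is "patient participant age, sex, duration of current episode of hip or knee pain, income, highest level of education, and comorbidity score". At site level it is "primary care site rurality and number of active patients (the covariates from the covariate-constrained allocation procedure". That makes eight covariates, none of which is a score for function or pain.

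The LEFS model brings in baseline by another route. Its fixed effects are "time, intervention group by time interaction (omitting the group main effect"), so the baseline wave is one of the repeated outcomes and the arms share a baseline mean. Pain, EQ-5D-5L and the psychosocial scores follow the same approach.

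Table 1 shows that the following are collected at baseline and at every follow-up: "LEFS, pain intensity, EQ-5D-5L, PSEQ, PCS, TSK-11, PHQ-2".

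**The concern.** An outcome with no baseline value cannot inherit the repeated-measures device that handles baseline in the LEFS model. When only the covariate list is carried over, baseline severity drops out of the GROC model altogether. Yet GROC asks how far symptoms or function have moved from where the patient began, and the starting point has been measured.

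The design makes a baseline difference plausible. Seven sites were allocated to each arm, and the constrained randomisation used only number of active patients and rurality. Sites were randomised in July 2023 and patients were recruited from October 2023. Medical secretaries and other providers identified them, and the plan says that blinding of primary care team members was not feasible. The plan acknowledges the risk: "A common concern in cluster RCTs is the risk of selection and recruitment bias, particularly when patient enrollment occurs after cluster assignment".

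At stake is the reading of one secondary comparison. A realised difference in severity would feed into the GROC odds ratio, and an adjustment added after that difference had been seen would look data-driven.

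**Working it through.** **1. The plan's own figure.** From Study Power: SD 16, ICC 0.1, cluster autocorrelation 0.5, individual autocorrelation 0.6, CV of cluster size 0.7, 20% attrition, 560 participants, 14 sites.
- Retained: 560 × 0.8 = 448, or 448/14 = 32 per site.
- Design effect: 1 + ((1 + 0.7²) × 32 − 1) × 0.1 = 5.67.
- Correlation of site means with baseline: (32 × 0.1 × 0.5 + 0.9 × 0.6)/(32 × 0.1 + 0.9) = 0.52.
- Variance of the 12-month difference: 2 × 16² × 5.67/(7 × 32) × (1 − 0.52²) ≈ 9.4, so SE ≈ 3.07 and 9/3.07 ≈ 2.93.
- Power (normal) ≈ 83%, or 77% with t on 12 df. The stated power above 80% is reproduced by the normal approximation. No power is stated for GROC.

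**2. Chance imbalance in baseline severity.** SE in SD units = √(2 × DE/(7 × 32)).
- Equal sites: DE = 1 + 31 × 0.1 = 4.1, SE = 0.19 SD, × 16 = 3.1 LEFS points.
- CV 0.7: DE = 5.67, SE = 0.23 SD, or 3.6 points.
- Probability of a difference of at least 0.2 SD: 30% to 37%; of at least 0.3 SD: 12% to 18%.
- At an assumed ICC of 0.05: 19% to 25% and 5% to 8%. At 0.01: 6% to 8% and about 1%.

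**3. Carry-over into the odds ratio.** The correlation r of GROC with baseline severity is not in the documents, so a range is assumed. On a latent logistic scale, a baseline difference of d SD gives an unadjusted log OR of about r × (π/√3) × d when the true OR is 1.

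| r | d = 0.2 | d = 0.3 |
|---|---|---|
| 0.1 | 1.04 | 1.06 |
| 0.2 | 1.08 | 1.11 |
| 0.3 | 1.11 | 1.18 |
| 0.5 | 1.20 | 1.31 |

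A negative r gives the reciprocals.

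**4. Power, illustrative linear simulation.** Latent GROC is set to Y12 − λY0 + noise, cut to −5..+5. Y0 and Y12 are standardised LEFS with site covariance 0.1/0.05 and individual covariance 0.9/0.54 (total correlation 0.59). There are 448 completers, gamma site sizes with CV 0.7, an effect of 9/16 SD, and a t-test on 12 df of site means with and without adjustment by the within-site baseline slope. λ = 1 means that GROC rates true change; λ = 0 means that it reflects present state only.

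| λ | Correlation with baseline (noise variance 0; 0.8 where derived) | Power, noise 0 | Power, noise 0.8 |
|---|---|---|---|
| 1 | −0.45; −0.32 | 76% → 86% | 67% → 78% |
| 0.8 | −0.25 | 83% → 86% | 72% → 74% |
| 0.59 | 0 | 85% → 85% | 74% → 73% |
| 0.3 | 0.34 | 84% → 86% | 71% → 72% |
| 0 | 0.59; 0.44 | 73% → 85% | 64% → 74% |

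Type I error was 4-7% with and without adjustment. The pattern follows the site-level variance, 0.1(1 + λ²) − 2λ × 0.05. This is 0.100 at λ = 0 or 1 and 0.079 at λ = 0.3. After adjustment with slope 0.54/0.9 = 0.6 it is 0.1 × 1.36 − 0.06 = 0.076. The gain therefore depends on how GROC weighs the starting point, and not on the overall correlation alone.

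**5. Standard error of the log OR.** A proportional-odds simulation (n = 448, no site effect, 150 runs, true log OR 0.5) gave an SE of 0.167 unadjusted and 0.170 adjusted at r = 0.5. Power rose from 72% to 87% because the unadjusted estimate was pulled toward zero (0.43 against 0.51). At r = 0.3, power was 83% in both.

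**The case against.** The best defence is that this is a pre-specified, cluster-aware secondary analysis with eight covariates, two of which (episode duration and comorbidity) are partial proxies for severity. Randomisation makes the comparison unbiased on average, chance imbalance is already in the standard error, and type I error is about the same either way. All of that stands. A reader might infer that the planned GROC test is invalid; the documents and the calculations do not support that.

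A reader might also infer that staff selected patients by severity. The plan describes efforts to invite consecutive patients, recruiting assistants unfamiliar with the patients, uniform criteria, identical information, and an arm not revealed until after consent. These reduce the risk without excluding it, and nothing in the documents shows that selection occurred. Adjustment would remove only the part that LEFS and NPRS measure.

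The size is uncertain, and even the sign is open: the assumed correlations run from −0.45 to 0.59. The linear simulation stands in for the ordinal model, omits the planned covariates, and shows gains of 10 to 12 points only at the two ends of its range. If GROC rates true change, a 3.3-point imbalance carries over as about (1 − 0.59) × 3.3 = 1.4 LEFS points, some 15% of the 9-point target. The plan itself calls an ICC of 0.1 conservative.

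Finally, LEFS and pain are analysed with baseline included, so a discordant GROC result would be noticed. That helps interpretation but does not correct the GROC estimate.

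**Conclusion.** The point holds as an inexpensive improvement to a secondary analysis. The GROC model contains no baseline severity measure, and the reason given (no baseline GROC) does not explain leaving out baseline LEFS and NPRS. With 7 sites per arm, a realised difference of 0.2 SD or more has a chance of roughly 30% to 37% at the plan's ICC, and clearly less at smaller ICCs. Its effect on the odds ratio is small at correlations of 0.1 to 0.2 and material near 0.5.

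The benefit is protection against imbalance and a possible gain in power. It should not be described as a smaller standard error of the log odds ratio, which did not shrink in the ordinal simulation. For patient satisfaction, a reader might infer the same benefit, but no correlation with severity is known and no gain is shown. The primary LEFS analysis is not affected.

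This rests on the Study Power inputs and on assumed links between GROC and baseline severity.

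**What to change.** In the Data Analysis Plan, before analysis starts and without reference to observed baseline differences by arm, extend the sentence on GROC so that the ordinal model adjusts for the existing covariates *and for baseline LEFS and baseline NPRS, each as a continuous term*. Keep the model without these two terms as a sensitivity analysis. The same terms may be added to the satisfaction model for consistency, with no gain claimed. Record the change through the registry, as the Protocol Amendments paragraph provides.

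The cost is one sentence and no new data. There are three minor downsides:
- The model has two more fixed effects.
- A rule is needed for a wholly missing baseline score (the plan's item-level mean imputation covers only missing items).
- The odds ratio becomes conditional on baseline severity as well as on the eight existing covariates, which the report should state.

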## Research Objectives:

- 1) To determine the effectiveness of a PT-led primary care model for people with hip and knee pain at

improving function (primary outcome), pain intensity, quality of life, global rating of change, patient satisfaction, and adverse events compared to usual physician-led primary care, when evaluated over a one-year period from the initial consultation.

2) To assess the impact of a PT-led primary care model for patients with hip and knee pain on the health system and society (healthcare access, primary care physician workload, healthcare utilization, missed work, cost-effectiveness), evaluated over a one-year period from initial consultation.

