## **2. Individual Health and Experience Outcomes**

The following individual health and experience measures are being collected through REDCap with repeat surveys at baseline, 3-, 6-, 9-, and 12-months post enrollment. Patient satisfaction, global rating of change, and adverse events are being collected at all follow-up time points only.

- Self-reported functioning: using the LEFS – a validated 20-item patient-reported outcome measure used to assess functional status related to lower extremity conditions. Each item is scored on a 5-point scale, with higher scores indicating better function.
- Pain intensity: measured using a Numeric Pain Rating Scale (NPRS) where 0 is no pain and 10 is the worst possible pain.
- Health-related quality of life: using the EuroQOL-5D (EQ-5D-5L), which is suitable for economic evaluations. The EQ-5D-5L score will also be converted to quality-adjusted life years (QALY).
- Global rating of change: using an 11-point global rating of change (GROC) scale to assess perceived overall change in health status, symptoms, or function over time, with anchors of a great deal better (+5) to a great deal worse (-5).
- Patient satisfaction: using an 11-point scale with anchors of very dissatisfied (-5) and very satisfied (+5).
- Adverse events: using an adverse events questionnaire aligned with reporting guidelines. The questionnaire determines: 1) adverse events experienced as a result of any of the interventions received; 2) a description of the adverse event; 3) duration of the adverse event; and 4) severity of the adverse event. Serious adverse events are identified if the participant requires hospitalization or an emergency department as a result of the adverse event, the adverse event leads to significant and persistent disability beyond 72 hours, or the adverse event is life-threatening. The study team monitored these responses to ensure ongoing patient participant safety.
- Potential mechanisms of the intervention:

- Self-efficacy: confidence in abilities to participate in usual activities using the Pain Self-Efficacy Questionnaire (PSEQ).

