to account for small number of clusters. Given that we have only included 14 clusters and adverse events are expected to be rare, we anticipate there may be issues of non-convergence or instability in our models. Should the model for adverse events not converge or demonstrate instability, we would attempt to fit the model using an independent working correlation matrix. If there are still issues of non-convergence or instability, we will reduce the model by removing covariates, beginning with duration of pain and income. Severity and duration of minor adverse events will be presented descriptively. We do not anticipate many, if any, serious adverse events; as such, we plan to present these data descriptively.

Visits with primary care physicians or nurse practitioners, time (days) lost from occupational activities, and assistance required (hours) will be presented as rates and compared by calculating rate ratios using GEE-type covariance estimators with an adjusted Poisson or negative binomial model, accounting for clustering, and assuming an exchangeable working correlation matrix. Incidence rates will be used to present visits to other health professionals within the primary care team, participation in group programs offered by the primary care team, and health care services received outside of the primary care team (medications, diagnostic imaging, walk-in clinic visits, ED visits, specialist physician visits, , hospital admissions, interventional procedures, surgeries, other health provider visits). Comparisons between groups for each of these variables will be made by calculating relative risk using robust Poisson regression. These models will incorporate empirical covariance (“sandwich”) bias-adjusted (residual-based) estimators, and the Fay and Graubard correction due to the small number of clusters. These models will use time as an offset to account for variable follow-up times. All of the healthcare utilization and lost time from occupational activity models will control for the same covariates as the patient health outcomes analyses. Similar to our analyses for adverse events, in the case of model non-convergence or instability, we will attempt to fit the model using an independent working correlation matrix and if the model still does not converge and demonstrate stability, we will reduce the model by removing covariates.

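### The only modelled comparison of adverse events covers minor events, with 'minor' undefined and no coding rule for a participant whose only event was serious; comparing any adverse event would close the gap

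*Combined protocol and SAP*

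**What the plan says.** The Research Objectives list the outcomes on which the two models are to be compared: "improving function (primary outcome), pain intensity, quality of life, global rating of change, patient satisfaction, and adverse events compared to usual physician-led primary care". Adverse events appear there as a whole.

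The section on individual health and experience outcomes defines the serious class in two parts. The first is use of acute care: "Serious adverse events are identified if the participant requires hospitalization or an emergency department as a result of the adverse event". The second is "the adverse event leads to significant and persistent disability beyond 72 hours, or the adverse event is life-threatening". That section does not define a minor event. On timing it says "Patient satisfaction, global rating of change, and adverse events are being collected at all follow-up time points only", which means 3, 6, 9 and 12 months.

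The Data Analysis Plan then splits the two classes:
- Minor events are modelled: "Incidence rates for minor adverse events (yes or no) will be calculated using robust Poisson regression and compared by calculating relative risks". The fallback for non-convergence is an independent working correlation, then removal of covariates.
- For their detail: "Severity and duration of minor adverse events will be presented descriptively".
- Serious events are not modelled: "We do not anticipate many, if any, serious adverse events; as such, we plan to present these data descriptively".

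The general rule at the head of the Data Analysis Plan is "All analyses will be by intention to treat principle". No rule is given for coding a participant who had a serious event and no minor one.

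**The concern.** The objective concerns adverse events, but the compared variable is a subset from which the worst events are removed by definition. An event that meets a serious criterion leaves the compared outcome. If one arm's events are more often serious, its compared risk falls for that reason alone. The relative risk then moves towards no difference, or in favour of the arm with the worse events.

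The serious class goes beyond hospitalization and threat to life. An emergency department visit because of the event is enough, and so is significant, persistent disability beyond 72 hours. The plan expects few serious events but gives no rate for them.

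At stake is whether the one adverse-event estimate with a confidence interval can be read as a comparison of harm. Blinding was not feasible and no data monitoring committee was set up, so this final analysis carries more weight than it otherwise might.

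**Working it through.** The plan gives no adverse event rate, no share of serious events and no power for harms, so there is no figure to reproduce. The check is a reading of the sections above plus arithmetic on assumed rates.

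**Inputs**
- From Study Power: 560 participants, 1:1 by site, taken as 560/2 = 280 per arm. This only sets the scale; the relative risks for coding 'no' depend on shares, not on the number per arm.
- Assumed: any-event risk q = 10% in both arms, so 28 affected participants per arm and an any-event relative risk (RR) of 1.00.
- Assumed: one yes/no value per participant over the year.
- Varied: s, the share of affected participants whose only event was serious.

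**Formulas**
- Serious-only coded 'no': risk = q(1 − s), so RR(minor) = (1 − s_PT)/(1 − s_UC).
- Serious-only excluded: risk = q(1 − s)/(1 − qs) in each arm, and RR is the ratio of the two.
- Any adverse event: RR = q/q = 1.00 throughout.

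**If serious events are as rare as the plan expects** (PT-led arm affected, none in usual care)
- One serious-only participant: coded 'no', 27/28 = 0.96; excluded, (27/279)/(28/280) = 0.97.
- Two: coded 'no', 26/28 = 0.93; excluded, (26/278)/(28/280) = 0.94.

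For scale, the RR of 26/28 has an approximate standard error on the log scale of √(1/26 − 1/280 + 1/28 − 1/280) = 0.259. That gives a 95% interval of about 0.56 to 1.54 before any allowance for clustering. The shift is small beside that imprecision.

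**If the criteria capture more events than expected**

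| Serious-only share, PT-led v usual care | Participants | RR, coded 'no' | RR, excluded |
|---|---|---|---|
| 10% v 0% | 2.8 v 0 | 0.90 | 0.91 |
| 20% v 5% | 5.6 v 1.4 | 0.80/0.95 = 0.84 | (0.08/0.98)/(0.095/0.995) = 0.855 |
| 50% v 5% (extreme) | 14 v 1.4 | 0.50/0.95 = 0.53 | 0.55 |

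**Two boundary cases.** If no event is serious, the minor-only and any-event analyses coincide. If every participant with a serious event also reports a minor one, RR(minor) stays at 1.00.

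The direction is therefore the same under either handling, and the size depends almost wholly on how many participants are serious-only.

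**The case against.** The best defence is that describing serious events is reasonable with 14 clusters and very few events expected, and that Objective 1 does not demand one pooled model. A modelled minor-event comparison plus reported serious events does address it in part. This stands, and it limits the point.

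A reader might infer three stronger things that the documents do not support:
- *That the plan codes a serious event as 'no'.* It states no coding rule. 'No' is the natural reading under intention to treat, since no exclusion is stated, but it remains an inference. A participant with both a minor and a serious event over the four surveys would still be 'yes' if the variable covers the year.
- *That serious events drop out of sight.* They are to be presented descriptively. Emergency department visits and hospital admissions are also compared between arms. That is a partial safeguard only: they are compared as healthcare utilization, are not tied to an adverse event, and do not capture the disability criterion.
- *That a large spurious benefit is likely.* The larger shifts above need 5 to 14 serious-only participants in one arm, well beyond the plan's expectation, and the descriptive table would show such an excess.

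Pooling also has a blind spot of its own. In every scenario above the any-event RR is 1.00 although seriousness differs between arms. Only the serious-event counts by arm reveal that difference, so pooling adds to them and cannot replace them.

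What the objection does not answer is the mismatch between objective and compared variable, the undefined term and the missing coding rule. Descriptive counts give no between-arm estimate or interval for adverse events as a whole.

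**Conclusion.** The point holds in limited form. The objective covers adverse events as a whole. The only modelled adverse-event comparison covers minor events, a class that is not defined, and the handling of serious-only participants is not stated. Under either plausible handling, a shift from minor to serious lowers an arm's compared risk.

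The likely effect is small: a minor-only RR of 0.96 or 0.93 against a true any-event RR of 1.00, for one or two serious-only participants in one arm. This rests on an assumed 28 affected per arm and one yes/no value per participant over the year. It becomes material, at 0.84 or lower, only if the serious criteria catch clearly more events in one arm than the plan expects.

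The documents do not support saying that the harm objective goes unanswered or that serious harms are concealed. Severity is minor to moderate, with moderate confidence, because the size depends on rates that the plan does not give.

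**What to change.** In the adverse-event paragraph of the Data Analysis Plan:
1. Change the compared outcome to any adverse event, minor or serious, yes or no. Keep the robust Poisson model, small-sample correction and fallback steps.
2. Define a minor event as any adverse event that meets none of the plan's own serious criteria, and state that the yes/no variable covers the whole follow-up year.
3. Report minor and serious counts by arm, with severity and duration for both classes, descriptively. At present severity and duration are promised only for minor events.
4. State that the pooled relative risk is to be read with the serious-event table, because it gives minor and serious events equal weight.

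The cost is wording only. The questionnaire already records whether an event occurred, its description, duration and severity, so no new data are needed. The any-event count cannot be lower than the minor-only count, so the expected convergence problem should not worsen for want of events, though the gain is slight if serious events are few. Analysis is to start only after data collection is complete, so the change can be made beforehand and recorded by the route in the Protocol Amendments paragraph.
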